#### **10.4.3 Local laboratory values**

Box plots of local laboratory values will be generated for baseline values and for values measured during the course of the study by treatment arm (Part A and Part B) and visit. Each box plot will show the first quartile, the median, and the third quartile. Outliers (values outside the box plot) will also be plotted. If appropriate, horizontal lines representing boundaries for abnormal values will be plotted.

For each local laboratory measure, summary statistics will be presented by treatment arm and time point, as well as changes from baseline for post enrollment values. In addition, the number (percentage) of participants with local laboratory values recorded as meeting Grade 1 AE criteria or above as specified in the Division of AIDS Table for Grading the Severity of Adult and Pediatric Adverse Events will be tabulated by treatment arm for each post vaccination time point. Reportable clinical laboratory abnormalities without an associated clinical diagnosis will also be included in the tabulation of AEs described above.

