5.1.1 Inclusion criteria

1. Able and willing to complete the informed consent process, including an Assessment of Understanding (AoU): volunteer demonstrates understanding of this study, completes a questionnaire prior to first vaccination with verbal demonstration of understanding of all questionnaire items answered incorrectly.
2. 18-50 years old, inclusive, on day of enrollment.
3. Agrees to comply with planned study procedures and be available for clinic follow-up through the last clinic visit.
4. Agrees not to enroll in another study of an investigational agent during participation in the trial, including severe acute respiratory syndrome coronavirus 2 (SARS-CoV-2) investigational agents that may subsequently obtain emergency use authorization (EUA) or undergo licensure by the FDA. If a potential participant is already enrolled in a SARS-CoV-2 clinical trial, prior approvals from the SARS-CoV-2 study sponsor and HVTN 303 PSRT are required prior to enrollment in HVTN 303.
5. In good general health without clinically significant medical history.
6. Physical examination and laboratory results without clinically significant findings that would interfere with assessment of safety or reactogenicity.

7. Body Mass Index (BMI) ≤ 40 .
8. Assessed as low risk for HIV acquisition as per [Appendix K](#), agrees to discuss HIV infection risks, agrees to risk reduction counseling, and agrees to avoid behavior associated with high risk of HIV exposure through the final study visit. Low risk may include persons stably taking pre-exposure prophylaxis (PrEP) as prescribed for 6 months or longer (see [Appendix K](#) for protocol safety review team [PSRT]) consultation requirements).
9. Suitable injection sites in the deltoid muscle of each arm, as assessed by a clinician.

Laboratory Criteria within 56 days prior to enrollment:

10. White blood cells (WBCs) 2,500-12,000/mm³
11. WBC differential either within institutional normal range or approved by the Investigator of Record (IoR) as “not clinically significant.”
12. Platelets = 125,000 – 500,000/mm³
13. Hemoglobin
 - ≥ 11.0 g/dL for volunteers who were assigned female sex at birth
 - ≥ 13.0 g/dL for volunteers who were assigned male sex at birth and transgender males who have been on hormone therapy for more than 6 consecutive months
 - ≥ 12.0 g/dL for transgender females who have been on hormone therapy for more than 6 consecutive months

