6.5.3.3 Local laboratory values

Box plots of local laboratory values will be generated for baseline values and for values measured during the course of the study by treatment arm (Part A and Part B) and visit. Each box plot will show the first quartile, the median, and the third quartile. Outliers (values outside the box plot) will also be plotted. If appropriate, horizontal lines representing boundaries for abnormal values will be plotted.

For each local laboratory measure, summary statistics will be presented by treatment arm and time point, as well as changes from baseline for post enrollment values. In addition, the number (percentage) of participants with local laboratory values recorded as meeting Grade 1 AE criteria or above as specified in the Division of AIDS Table for Grading the Severity of Adult and Pediatric Adverse Events (Section 9.1) will be tabulated by treatment arm for each post vaccination time point. Reportable clinical laboratory abnormalities without an associated clinical diagnosis will also be included in the tabulation of AEs described above.

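### The graded laboratory count takes no account of each participant's pre-vaccination grade, so it cannot separate new abnormalities from pre-existing ones

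*SAP*

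**What the plan says.** SAP 10.4.3 plans three displays of local laboratory data.

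- Box plots by arm and visit: "Box plots of local laboratory values will be generated for baseline values" as well as for values during the study.
- Summary statistics for each measure by arm and time point, "as well as changes from baseline for post enrollment values".
- A graded count: "the number (percentage) of participants with local laboratory values recorded as meeting Grade 1 AE criteria or above". Protocol 6.5.3.3 has the same rule and says that this count "will be tabulated by treatment arm for each post vaccination time point".

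A separate sentence links laboratory values to the adverse event tables: "Reportable clinical laboratory abnormalities without an associated clinical diagnosis will also be included in the tabulation of AEs described above".

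Two entry criteria in protocol 5.1.1 bear on the point. Item 11 requires a "WBC differential either within institutional normal range or approved by the Investigator of Record (IoR) as" clinically unimportant, and sets no numeric or grade ceiling. Item 6 requires "laboratory results without clinically significant findings that would interfere with assessment of safety or reactogenicity". Eligibility laboratory tests may be up to 56 days old at enrolment. The schedules in the protocol appendices also draw CBC with differential and ALT/creatinine on Day 0 in both parts.

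**The concern.** The graded count has no baseline condition, no baseline column and no cross-classification by baseline grade. A participant at Grade 1 on Day 0 who stays there is counted at each later visit in the same way as one who moved from normal to Grade 1 after dosing.

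Three features make this matter more here than in a larger controlled trial.

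- Safety laboratory measures are part of primary endpoint 1.
- There is no placebo product (protocol 9.2.1), so each participant's own pre-dose value is the natural reference.
- Arms have 3, 9 or 10 participants, so one person moves a percentage a long way.

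The protocol's opening summary lists transient rises in eosinophil count among the trends that the safety review team saw before vaccination was stopped. Eosinophils belong to the differential, the one haematology measure that the entry criteria leave without a numeric limit.

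**Working it through.** **Inputs from the documents.** Arm sizes are 3 in each Part A group and 10, 10 and 9 in Groups 6, 7 and 8. The counting rule is the one in SAP 10.4.3.

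**Input that is assumed.** Let q be the share of participants at Grade 1 or above on one given analyte before dosing whose value persists at the visit in question. The documents give no figure, so q is taken over 2% to 20%.

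**Check of the tool.** The laboratory section states no figure to reproduce. The same binomial formula underlies SAP Table 6-1, so it was run against that table for n = 3, 9 and 10 at rates of 1% to 30% and for n = 44 at 1% to 10%. Every cell checked agreed to the printed decimal. For example, n = 10 at 5% gives 1 − 0.95^10 = 40.1%, as printed.

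**Step 1: weight of one participant.** 1/3 = 33 percentage points, 1/9 = 11 and 1/10 = 10, at each visit where the value is still Grade 1 or above.

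**Step 2: chance that an arm shows a count when nothing new has happened.** P(at least 1) = 1 − (1 − q)^n.

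| Arm size | q = 2% | q = 5% | q = 10% | q = 20% |
|---|---|---|---|---|
| 3 | 5.9% | 14.3% | 27.1% | 48.8% |
| 9 | 16.6% | 37.0% | 61.3% | 86.6% |
| 10 | 18.3% | 40.1% | 65.1% | 89.3% |

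In an arm of 10 the expected number carried over is 10q, or 0.2 to 2.0 participants. If only grades above the Day 0 grade are counted, every entry becomes 0.

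**Step 3: effect on the reported percentage.** Suppose, for illustration, that 10% of the participants who were not graded at baseline become graded, and that those graded at baseline neither improve nor worsen. The rule as written gives an expected rate of q + (1 − q) × 0.10. Counting new grades only gives (1 − q) × 0.10.

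| q | As written | New grades only |
|---|---|---|
| 2% | 11.8% | 9.8% |
| 5% | 14.5% | 9.5% |
| 10% | 19.0% | 9.0% |
| 20% | 28.0% | 8.0% |

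**Step 4: do the other displays fill the gap?** Box plots and change-from-baseline statistics summarise a continuous value by arm. Neither shows whether a particular participant in the graded count had the same grade on Day 0. SAP 11.2 to 11.4 list only one laboratory output, the box plots; no graded or shift table appears there.

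**The case against.** The strongest reply is that this is a descriptive display that drives no test, threshold or decision. Baseline is not absent from the section, and with so few participants a baseline outlier would usually be visible in the box plots. That is fair, and it limits the weight of the point. It does not close the gap, because the plots do not link a participant's values across visits.

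A reader might also infer more than the documents support.

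- *That pre-existing abnormalities are reported as adverse events.* The table counts participants with graded values at a time point. Only reportable abnormalities go to the adverse event tables, which are also broken down by severity or relationship to product. The documents do not say how baseline affects what is reportable, so this inference is not shown.
- *That the entry rules admit Grade 1 values.* Outside the institutional range is not the same as Grade 1. Protocol 9.1 names the grading scale without reproducing its cut-offs. Item 6 excludes clinically significant findings that would interfere with safety assessment, and white cells, platelets and hemoglobin have numeric limits. ALT and creatinine may exceed the upper limit of normal at entry, but nothing shows that the permitted values are gradable, so they are not relied on here.
- *That eosinophil rises caused the stop.* The opening summary lists them among several trends. It says that certain events led to pauses and that the board reviewed all safety data; it does not attribute the decision to eosinophils.
- *That a carried-over participant inflates every visit.* This holds only where the value stays at Grade 1 or above.

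**Conclusion.** The concern holds in a limited form. The graded count in SAP 10.4.3 and protocol 6.5.3.3 ignores pre-vaccination grade, and no other planned display separates new from pre-existing grades for individual participants. Carry-over is possible under item 11 and the 56-day eligibility window, but it is not demonstrated. The weight of one participant follows from the arm sizes alone. The probabilities rest wholly on the assumed q for a single analyte and on persistence at the visit, and the width of the range (18% to 89% in an arm of 10) shows how little the documents settle. This is an inexpensive improvement to a descriptive display and does not put any planned inference in doubt.

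**What to change.** In SAP 10.4.3 and protocol 6.5.3.3, add for each analyte a shift table by arm. It should set Day 0 grade (the last pre-vaccination value if Day 0 is missing) against worst post-vaccination grade. Count as treatment-emergent only those participants whose post-vaccination grade exceeds their Day 0 grade. Name absolute eosinophil count as one of the analytes; if the grading scale gives no grade for it, show each participant's Day 0 and peak values instead. Keep the present per-visit count as supportive. State how baseline enters the decision that an abnormality is reportable. List the new table in SAP 11.2, which at present lists no graded laboratory table.

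The cost is a few sentences of text and one further table. CBC with differential and ALT/creatinine are already collected on Day 0, so no new sample, visit or data item is needed.

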HIV VACCINE
TRIALS NETWORK

PROTOCOL

HVTN 303

A Phase 1, Open-Label Clinical Trial to Evaluate Safety, Tolerability, and Immunogenicity of Adjuvanted HIV-1 Fusion Peptide Conjugate Vaccine (VRC-HIVVCP0108-00-VP) Alone or in Prime-Boost Regimens with Adjuvanted HIV-1 Envelope Trimer 4571 (VRC-HIVRGP096-00-VP) and HIV-1 Trimer 6931 (VRC-HIVRGP0106-00-VP) Vaccines in Healthy Adults

DAIDS DOCUMENT ID 38835

IND 028412 HELD BY DAIDS

CLINICAL TRIAL SPONSORED BY

Division of AIDS (DAIDS)
National Institute of Allergy and Infectious Diseases (NIAID)
National Institutes of Health (NIH)
Department of Health and Human Services (DHHS)
Bethesda, Maryland, USA

STUDY PRODUCTS PROVIDED BY

Vaccine Research Center (VRC)
NIAID, NIH, DHHS
Bethesda, Maryland, USA

September 21, 2023

Final
HVTN 303
Version 2.0

HVTN 303 enrolled (vaccinated) its first participant on August 15, 2022, with the goal to enroll 60 participants in the study. As of Dec 20, 2022, 44 participants were enrolled (no enrollments occurred after this date). Part A (Groups 1, 2, 3, 4, and 5) completed enrollment of 15 participants from August 15 to October 14, 2022.

Part B enrolled 29 participants from November 3 to December 20, 2022: Group 6 enrolled 10 ppts, all of whom received 1 vaccination; Group 7 enrolled 10 participants, 5 of whom received 2 vaccinations; Group 8 enrolled 9 participants, 6 of whom received 2 vaccinations. No participants received a 3rd vaccination.

Over time, the PSRT observed trends in local and systemic reactogenicity (grade 3 fever, grade 3 injection site erythema, and/or induration/swelling), unsolicited adverse events (urticaria, rash, and serum sickness), and temporary increases in absolute eosinophil counts (AECs) post-vaccination. Certain of these events resulted in pauses in all vaccinations, and the PSRT requested the HVTN Safety Monitoring Board (SMB) perform an ad hoc review of all safety data. Following this review on January 11, 2023, the SMB recommended that all vaccinations in the study be permanently discontinued, and that participants be continued in safety follow-up, and these recommendations were implemented.

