2.6 Assessment of Immunogenicity

Vaccinations were stopped on January 13, 2023, resulting in most (33) participants receiving only 1 vaccination and eleven participants in Groups 7 and 8 receiving 2 vaccinations. Specimens to evaluate immunogenicity were collected at baseline and at the specified timepoints after the administration of product until March 13, 2023, when the FDA informed DAIDS that the IND has been placed on Clinical Hold and confirmed that all protocol-related activities must cease except for any participant safety follow-up assessments. The primary immunogenicity time point, after the changes to the vaccination and collection schedule, remains 2 weeks after the last vaccination, however participants only received 1 or 2 vaccinations. Antibody titers will be measured by Electrochemiluminescence (ELICA) using a Meso Scale Discovery (MSD) platform for all participants with one or two vaccinations in Groups 5, 6, 7 and 8.

Additional exploratory assays to assess humoral and cellular immune responses may be performed, including B cell response and neutralization antibody assays.

A specimen collection has been added at approximately 10 months post the

Specimens to evaluate immunogenicity will be collected at baseline and at specified time points throughout the study after the administration of product. HIV-specific humoral immune responses will be assessed by neutralization antibody assays. The primary immunogenicity time point is 2 weeks after the last vaccination.

Trimer 4571- and Trimer 6931-specific antibody titers will be measured by Electrochemiluminescence (ELICA) using a Meso Scale Discovery (MSD) platform. Other exploratory assays to assess humoral and cellular immune responses may be performed with stored samples.

Measurements of antibody, B-cell and T-cell responses may be assessed from stored samples for timepoints throughout the study as exploratory evaluations. This includes a number of high-throughput functional assays and high-throughput biophysical profiling tools to comprehensively characterize the humoral immune response elicited by vaccination regimens.

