Appendix F Follow up visit windows post termination of vaccination

Visit windows for Part A (Groups 1-5)						
Visit Number	Visit Type	Lower Allowable Window (-)	Lower Target Window (-)	Target Day*	Upper Target Window (+)	Upper Allowable Window (+)
01	Screening	-56	-	0	-	+0
02	Enrollment/Vaccination 1	-	-	0	-	-
03	1-week post-vaccination 1	-2	-1	7	+1	+3
04	2 weeks post-vaccination 1 Primary Immunogenicity	-4	-2	14	+2	+7
05	Follow-up	-7	-2	28	+2	+7
06	Follow-up	-7	-3	56	+3	+7
07	Follow-up	-7	-3	84	+3	+7
08	Follow-up	-14	-3	112	+3	+14
09	Follow-up	-14	-7	168	+7	+14
10	Follow-up	-14	-7	224	+7	+14
11	Follow-up	-14	-7	280	+7	+14
12	Final Visit	-21	-14	364	+14	+21

* All target dates are relative to Day 0.

Visit windows for Part B (Group 6)						
Visit Number	Visit Type	Lower Allowable Window (-)	Lower Target Window (-)	Target Day*	Upper Target Window (+)	Upper Allowable Window (+)
100	Screening	-56	-	0	-	+0
101	Enrollment/Vaccination 1	-	-	0	-	-
102	1-week post-vaccination 1	-2	-1	7	+1	+3
103	2 weeks post-vaccination 1	-4	-2	14	+2	+14
110	Follow-up visit	-14	-3	84	+3	+14
111	Follow-up visit	-2	-1	91	+1	+3
112	Follow-up visit	-4	-2	98	+2	+14
116	Follow-up visit	-21	-3	168	+3	+21
117	Follow-up visit	-2	-1	175	+1	+3
118	Follow-up visit	-4	-2	182	+2	+14
122	Follow-up visit	-21	-3	252	+3	+21
123	Follow-up visit	-2	-1	259	+1	+3
124	Follow-up visit	-4	-2	266	+2	+14
129	Follow-up visit	-21	-3	336	+3	+21
130	Follow-up visit	-2	-1	343	+1	+3
131	Follow-up visit	-4	-2	350	+2	+14
132	Follow-up visit	-28	-3	392	+3	+28

*Target dates are relative to Day 0 (Enrollment), with the exception of post-vaccination visits, which are relative to the prior vaccination visit.

Visit windows for Part B (Group 7)						
Visit Number	Visit Type	Lower Allowable Window (-)	Lower Target Window (-)	Target Day*	Upper Target Window (+)	Upper Allowable Window (+)
100	Screening	-56	-	0	-	+0
101	Enrollment/Vaccination 1	-	-	0	-	-
102	1-week post-vaccination 1	-2	-1	7	+1	+3
103	2 weeks post-vaccination 1	-4	-2	14	+2	+7
104	Vaccination 2	-6	-3	28	+3	+7
105	1-week post-vaccination 2	-2	-1	35	+1	+3
106	2 weeks post-vaccination 2	-	-2	42	+2	-
107	Follow-up visit	-6	-3	56	+3	+7
108	Follow-up visit	-2	-1	63	+1	+3
109	Follow-up visit	-	-2	70	+2	-
110	Follow-up visit	-6	-3	84	+3	+14
111	Follow-up visit	-2	-1	91	+1	+3
112	Follow-up visit	-4	-2	98	+2	+14
116	Follow-up visit	-21	-3	168	+3	+21
117	Follow-up visit	-2	-1	175	+1	+3
118	Follow-up visit	-4	-2	182	+2	+14
122	Follow-up visit	-21	-3	252	+3	+21

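### Laboratory summaries by arm and visit do not separate one-dose from two-dose participants in Groups 7 and 8, so they cannot show what a second dose does

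*SAP*

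**What the plan says.** SAP 10.4.3 sets three laboratory displays. Box plots are drawn "by treatment arm (Part A and Part B) and visit". Summary statistics follow the same grouping; in the wording of protocol 6.5.3.3, "summary statistics will be presented by treatment arm and time point, as well as changes from baseline for post enrollment values". The number and percentage of participants at Grade 1 or above "will be tabulated by treatment arm for each post vaccination time point". SAP 10.1 keeps every enrolled participant in the randomised arm, whatever number of doses was given.

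On exposure, the summary at the front of protocol version 2.0 states "Group 7 enrolled 10 participants, 5 of whom received 2 vaccinations" and "Group 8 enrolled 9 participants, 6 of whom received 2 vaccinations". Protocol 2.6 gives the overall split: stopping vaccination came early, "resulting in most (33) participants receiving only 1 vaccination and eleven participants in Groups 7 and 8 receiving 2 vaccinations".

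Appendix F, written for the period after termination, still labels Visit 105 in both groups "1-week post-vaccination 2" and Visit 106 the corresponding 2-week visit. Appendix D shows CBC/differential and ALT/creatinine at both visits for the whole group. The collections it limits to two-dose participants are leukapheresis and the 204 mL draw that replaces it.

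**The concern.** Eight of the 19 participants in Groups 7 and 8 (5 + 3) never had dose 2. If their Day 35 and Day 42 blood results enter a column headed as post-vaccination 2, that column mixes two different exposures. A percentage or mean in it is pulled toward the one-dose level, and no reader of the table could tell by how much.

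This matters because laboratory safety is part of primary endpoint 1, and temporary rises in absolute eosinophil count are among the trends listed in the front summary before the stop. Whether laboratory values behave differently after a second dose is a natural question for the final safety report. Only these 11 participants can inform it.

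The plan already recognises the distinction elsewhere. Protocol 6.2.1 sizes the immunogenicity evaluation separately after dose 1 (9 in each of Groups 7 and 8) and after dose 2 (4 and 5). The SAE listing in SAP 10.4.2 reports the number of vaccinations and the time since the last one. The laboratory section does neither.

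**Working it through.** **Inputs.** Enrolled: 15 (Part A), 10 (Group 6), 10 (Group 7), 9 (Group 8). Dose-2 recipients: 5 (Group 7), 6 (Group 8). Source: front summary of protocol version 2.0.

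**Reproducing the plan's figures.** Two doses: 5 + 6 = 11. One dose: 15 + 10 + 5 + 3 = 33. Total 44, matching protocol 2.6. The event rate giving a 90% chance of at least one event is 1 - 0.1^(1/n): 20.6% for n = 10 and 22.6% for n = 9, matching SAP section 9.

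**Are one-dose values at these visits plausible?** Part B enrolled from 3 November to 20 December 2022. Day 35 for the first participant is 8 December 2022; Day 42 for the last is 31 January 2023. The front summary says safety laboratory follow-up ran at least 7 months after last vaccination for all of Part B. Letter of Amendment 4, which removed future safety blood draws, is dated 31 July 2023. So such values are plausible, but the documents do not give attendance.

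**Dilution.** Let m be the dose-2 recipients with a value, k the one-dose participants with a value, p2 the rate after dose 2 and p1 the one-dose rate at the same visit.

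- Rate shown = (m·p2 + k·p1)/(m + k)
- Share of the excess p2 - p1 that is lost = k/(m + k)

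| k | Group 7 (m = 5) | Group 8 (m = 6) |
|---|---|---|
| 0 | 0% | 0% |
| 1 | 16.7% | 14.3% |
| 2 | 28.6% | 25.0% |
| 3 | 37.5% | 33.3% |
| 4 | 44.4% | - |
| 5 | 50.0% | - |

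**Effect on the raw percentage**, with full attendance and an assumed p2 of 60%:

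| Assumed p1 | Group 7 shown (loss) | Group 8 shown (loss) |
|---|---|---|
| 0% | 30.0% (50%) | 40.0% (33%) |
| 10% | 35.0% (42%) | 43.3% (28%) |
| 20% | 40.0% (33%) | 46.7% (22%) |

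The excess over p1 still shrinks by exactly one half and one third in every row.

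**Box-plot medians** (simulation, normal values with a common SD, full attendance). In Group 7 a shift is halved. In Group 8 an assumed shift of 1, 2 or 3 SD appears as 0.68, 1.46 or 2.37 SD, a loss of 32%, 27% or 21%.

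**What the correct denominators can detect.** With n = 5 and n = 6, the rate giving a 90% chance of at least one event after dose 2 is 36.9% and 31.9%, against 20.6% and 22.6% for the full arms.

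**The case against.** The best reply is that no text places a one-dose participant in a post-dose-2 time point. The Grade 1 rule speaks of post-vaccination time points, and Appendix F counts post-vaccination visits from the preceding vaccination, so a person without dose 2 has no anchor for such a visit. The Appendix D grid also ticks the second vaccination and its diary for the whole group, so its ticks do not prove who attended or was bled. Appendix C carried a footnote redirecting participants who stop injections, though the visit numbers it cites do not occur in the Part B grids.

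Part of this stands: the pooling follows from reading the rules literally and is not stated. But the narrow reading covers at most the Grade 1 table. The box plots are by visit, and they are the only dedicated laboratory display in the SAP's lists of tables and figures (11.2, 11.4). Nor does the narrow reading say where the one-dose values go.

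It is also fair that signals are not hidden entirely. Outliers are plotted individually, reportable abnormalities enter the AE tables, and product administration frequencies are tabulated. None of these supplies a dose-2 denominator, and the AE tables too are by arm.

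A reader might infer that the eosinophil signal itself is halved. The documents do not support that. The rise is described only as following vaccination, with no dose number, and a rise after dose 1 at Visits 102 and 103 would not be diluted.

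**Conclusion.** The gap is real and worth closing. As written, the laboratory summaries for Groups 7 and 8 can mix one-dose and two-dose participants at Visits 105 and 106, and so cannot show whether a second dose changes laboratory values. The excess over the one-dose rate is understated by up to 50% in Group 7 and up to 33% in Group 8. Both maxima assume that all dose-2 recipients and all one-dose participants have a value at the visit. With fewer one-dose values the loss falls, to zero if none has one. For the raw percentage to fall by the same amounts, no one-dose participant may show the abnormality.

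Three stronger inferences should be avoided:

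- **A fixed Group 7 versus Group 8 distortion.** With full attendance and no one-dose events, a common rate p would show as 0.50p and 0.67p, a ratio of 1.33. If only Group 8's one-dose participants attended, it would show as 1.00p and 0.67p, reversing the order.
- **Bias always toward no effect.** The pull is toward the one-dose rate. If, for illustration, 1 of 5 two-dose and 2 of 5 one-dose participants were abnormal, pooling gives 3/10 = 30% against 20%. The documents do not say why each dose 2 was missed.
- **Falsely narrow confidence limits.** SAP 10.4.3 promises no intervals for laboratory values.

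**What to change.** In SAP 10.4.3, mirrored in protocol 6.5.3.3, for Groups 7 and 8 from Visit 104 onward:

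1. Present laboratory tables and box plots separately by doses actually received (one or two), indexed by time since the most recent dose.
2. Use as the post-dose-2 denominator only dose-2 recipients with a value, at most 5 in Group 7 and 6 in Group 8, and print it in each cell.
3. Show one-dose participants' Visit 105, Visit 106 and later values in their own column, and carry the later follow-up visits in both columns.
4. State that the two-dose subset is not a randomised group and is described only.

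If the sponsor already intends post-vaccination 2 to cover dose-2 recipients only, items 2 and 3 put that in writing. The cost is SAP wording and a re-cut of data already collected. The downside is smaller denominators and a few more columns.
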